## 7.3. DERIVED TIMEPOINTS

The last non-missing post-OL Baseline (i.e., post first OLE dose) measurement collected up to and including the Visit 14E (EOT/ET) measurement and within 7 days post the last OLE dose will be carried forward and defined as the last observation carried forward (LOCF) endpoint. Both scheduled and unscheduled assessments as well as the early termination assessments that are collected during this period will contribute to the derivation of the LOCF endpoint. However, scheduled and unscheduled measurements taken after the Visit 14E (EOT/ET) measurement or beyond 7 days post the last OLE dose will not be used in the derivation.

The study visits will be mapped to analysis visits for table summaries (Table 1).

**Table 1: Mapping of study visits to analysis visits.**

Study Visit	Analysis Visit Number	Analysis Visit
NA*	0	DB Baseline
Visit 1E	1	OL Baseline
Visit 1EJ#	1.1	OL Day 1
Visit 2E	2	OL Week 2
Visit 3E	3	OL Month 1
Visit 4E	4	OL Month 2
Visit 5E	5	OL Month 3
Visit 6E	6	OL Month 4
Visit 7E	7	OL Month 5
Visit 8E	8	OL Month 6
Visit 9E	9	OL Month 7

Visit 10E	10	OL Month 8
Visit 11E	11	OL Month 9
Visit 12E	12	OL Month 10
Visit 13E	13	OL Month 11
Visit 14E (if representing true EOT visit). For ET visit mapping see Section 7.4	14	OL Month 12
Visit 15E	15	Follow-up

\* Several assessments from that visit are collected in SEP380-301 study. #An extra visit for Japan (Visit 1EJ) on Day 1 that evaluates ECG.

Original study visit collected on the case report forms (CRFs) will be displayed in the listings.

## 7.4. RETESTS, UNSCHEDULED VISITS, AND EARLY TERMINATION DATA

In general, for by-visit summaries, data recorded at the planned visits where assessment is intended to be given and collected within 7 days post the last OLE dose will be presented, as well as the derived DB and OL Baseline values and the LOCF value.

Unscheduled measurements will not be included in by-visit summaries as a separate time point. However:

- Unscheduled measurements collected prior to the first dose of study medication in SEP380-301 contributed to the derivation of the DB Baseline value.
- Unscheduled measurements collected in SEP380-301 or SEP380-303 prior to the first dose of OLE study medication in SEP380-303 will contribute to the derivation of the OL Baseline value.
- Unscheduled measurements collected post-OL Baseline up to and including 7 days post the last OLE dose in SEP380-303 will contribute to the derivation of the LOCF value, the potential clinically significant (PCS) value, and the best/worst case value where required (e.g., shift table).

In the case of a retest, the assessment recorded under the planned visit will be used for by-visit summaries, and the assessment(s) recorded under unscheduled visit(s) will be presented in listings only.

As per protocol, study Visit 14E can be a Week 52/End of Treatment (EOT) visit or an Early Termination (ET) visit. If a subject terminates early, his/her measurements taken at the ET visit and within 7 days post the last OLE dose will be mapped to the next planned visit (after the last scheduled visit the subject attended) during which that assessment was expected to be performed as specified by the Schedule of Assessments table in the protocol. This applies to both efficacy and safety data. ET measurements taken beyond 7 days post the last OLE dose will not be mapped.

Listings will include scheduled, unscheduled, retest, and early discontinuation data without regard to the 7-day window, with original dates and visits displayed.

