22. APPENDIX III. BLOOD SAMPLE COLLECTION AND HANDLING GUIDELINES FOR PHARMACOKINETIC AND PLASMA PROLACTIN ASSESSMENTS

Please refer to the Laboratory Investigator Manual for all collection and shipping instructions.

Visit No.	Time	Aramisulpride and Esamisulpride PK and Plasma Prolactin Blood Sample Collection Times:
1E	Baseline (Day -1)	Carried over from 6-week double-blind placebo- controlled lead-in study of SEP-4199 CR
2E	Week 2 (± 2 days)	Postdose*
4E	Month 2 (\pm 5 days)	Postdose*
6E	Month 4 (\pm 5 days)	Postdose*
8E	Month 6 (\pm 5 days)	Postdose*
10E	Month 8 (± 5 days)	Postdose*
12E	Month 10 (\pm 5 days)	Postdose*
14E	Month 12 (+ 5 days)	Postdose*
15E	7 ± 2 days after last dose	Follow-up**

Blood must be collected from all subjects at the time points indicated below.

* Sample will be collected after dosing is given on that day. Actual date and time will be recorded.

** Actual date and time will be recorded.

COLLECTION REQUIREMENTS:

Collect 4 mL blood sample into a K₂EDTA (ethylenediaminetetraacetic acid) treated Vacutainer[®] (or equivalent) tube at each time point. Invert gently 8 to 10 times to mix well. Keep the blood collection tube on wet ice prior to centrifugation, and centrifuge for 10 minutes at approximately x 1500 g to isolate plasma within 30 minutes of blood collection. To ensure a more homogenous sample, all plasma samples should first be transferred to 1 tube and mixed well (by repeatedly aspirating and dispensing the sample into the storage tube). Split the sample with approximately equal volume into 2 polypropylene tubes, and label as Set-1 and Set-2. Store plasma tubes at approximately -20°C or lower freezer within 1 hour until shipping to the bioanalytical lab. The date and time of blood collection must be recorded.

All samples will be shipped with dry ice protection. Set-1 samples will be shipped to the Bioanalytical Lab for aramisulpride and esamisulpride concentration measurements and Set-2 samples will be shipped to another lab for prolactin concentration measurement.

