## 7.5. WINDOWING CONVENTIONS

No visit windowing will be performed during the analysis for this study. Data will be analyzed according

to the schedule outlined in the CSP. However, with the exception of SAE and PWC, any data collected beyond 7 days post the last OLE dose will be excluded from the efficacy and safety analyses unless otherwise specified; these data will be presented in data listings only.

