### 18.2. LABORATORY EVALUATIONS

Results from the central laboratory to be reported for this study include Hematology, Chemistry (including lipid panel and thyroid panel), Urinalysis, Urine drug screening, Serum pregnancy ( $\beta$ -HcG) (in

female subjects only), and Urine pregnancy (in female subjects only).

Serum and urine pregnancy results in female subjects and any unexpected lab parameters not specified in protocol Section 21 (APPENDIX II. CLINICAL LABORATORY TESTS) will only be listed. Laboratory parameters prespecified in protocol Section 21 under the categories of "HEMATOLOGY", "BLOOD CHEMISTRIES" (plus HOMA-IR), "URINALYSIS", and "URINE DRUG SCREENING" will be summarized in tables as well as presented in listings.

Listing presentations will use both standard international (SI) Units and conventional units. Table summaries will also be provided using both SI units and conventional units.

Quantitative laboratory measurements reported as "< X", i.e., below the lower limit of quantification (BLQ), or "> X", i.e., above the upper limit of quantification (ULQ), will be converted to X for the purpose of quantitative summaries, but they will be presented as recorded, i.e., as "< X" or "> X" in the listings.

The following summaries will be provided:

- For quantitative measurements in hematology, chemistry, and urinalysis: By-visit summary of observed values at DB Baseline, OL Baseline, each scheduled OLE study visit (starting from Visit 2E), and LOCF; by-visit summary of change from DB Baseline at each scheduled OLE study visit (starting from Visit 1E) and LOCF; by-visit summary of change from OL Baseline at each scheduled post-OL Baseline extension study visit (starting from Visit 2E) and LOCF.

Serum prolactin results will be summarized overall and separately by sex. Glucose, insulin, HOMA-IR, and lipid panel results (total cholesterol, LDL cholesterol, HDL cholesterol and triglycerides) will be summarized by fasting status: fasting only and overall (fasting, non-fasting, or fasting status unknown combined).

Change from DB Baseline for glucose, insulin, HOMA-IR, and lipid panel results will only be calculated if the fasting status at a given OLE study visit is matching the fasting status at DB Baseline. Change from OL Baseline will only be calculated if the fasting status at a given post-OL Baseline extension study visit is matching the fasting status at OL Baseline.

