## 19. PHARMACOKINETIC ANALYSIS

All PK analysis will be performed using Safety population.

Blood sample for plasma concentrations of R-amisulpride, S-amisulpride, total amisulpride, and/or plasma prolactin measurement will be collected at: Visit 1E (coinciding with Visit 9 of SEP380-301), Visit 2E, Visit 4E, Visit 6E, Visit 8E, Visit 10E, Visit 12E, Visit 14E, and Visit 15E/Follow-up. Any plasma concentration or summary statistics below the lower limit of quantification (LLOQ) will be represented by "BLQ" (below the limit of quantification) in tables and listings. Amisulpride plasma concentration will not

be presented for the placebo group.

R-amisulpride, S-amisulpride, total amisulpride, and plasma prolactin concentrations at each scheduled sample collection time point (including ET and Follow-up, see [Section 7.4](#) for mapping of the ET visit) will be summarized descriptively (n, mean, median, minimum, maximum, coefficient of variation [CV] and if appropriate, geometric mean and geometric CV [GCV]). In addition, if there is at least 1 concentration < LLOQ within a treatment group at a time point, it will be set to  $\frac{1}{2}$  LLOQ for summary statistics calculations. Number and percentage of concentrations that are below the LLOQ will be provided for each visit. All PK summaries will be presented.

Population PK analysis methods will be used to characterize the PK/PD profiles in subjects treated with SEP-4199 CR. Analysis methods and results of population PK and PD analysis will be described in a separate document from the SAP and clinical study report.

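### The early termination mapping in SAP 7.4 and 19 can place off-drug PK and plasma prolactin samples, and values well ahead of schedule, under on-treatment visit labels

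*SAP*

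**What the plan says.** SAP 7.4 states that, for a subject who stops early, ET measurements up to 7 days after the last open-label dose "will be mapped to the next planned visit (after the last scheduled visit the subject attended") at which that assessment was due. The count starts from the last scheduled visit attended; the study day of the ET measurement plays no part. The section adds: "This applies to both efficacy and safety data". ET data later than 7 days after the last dose are not mapped.

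SAP 19 summarises R-, S- and total amisulpride and plasma prolactin "concentrations at each scheduled sample collection time point (including ET and Follow-up"), and refers to SAP 7.4 for the ET mapping. That cross-reference is what brings PK data under the rule. Serum prolactin comes under it directly as a safety laboratory test. SAP 18.2 says of it: "Serum prolactin results will be summarized overall and separately by sex".

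SAP 7.5 removes any check on study day: "No visit windowing will be performed during the analysis for this study".

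Protocol Appendix III (Section 22) describes the PK and plasma prolactin samples at Visits 2E to 14E as postdose: "Sample will be collected after dosing is given on that day". It lists a separate Follow-up sample at Visit 15E, 7 ± 2 days after the last dose.

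**The concern.** A by-visit concentration table is read as showing levels on drug at that month. If some entries come from subjects who stopped dosing days earlier, the table mixes two states without saying so. The same off-drug interval could appear as OL Month 4 for one subject and as Follow-up for another, depending only on the name of the visit.

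Timing is a second problem. Some assessments are scheduled two or six months apart, and the rule moves an ET value forward to the next slot whatever the distance. A value after short exposure can then be shown as one after longer exposure.

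The displays are descriptive, so the labels carry the meaning. Only 64 subjects were enrolled (SAP 4.4), split into two groups plus a total, so cells are small. SAP 4.7 cites early termination of the study, and Protocol Section 14 sends subjects in a terminated study through the ET visit. ET records may therefore be common, although neither document says how many there are.

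**Working it through.** The plan gives no figure of its own to reproduce here. The check applies the rule to the schedule of assessments.

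**Off-drug overlap.** ET data are mapped at 0 to 7 days after the last dose (SAP 7.4). The Follow-up window is 7 − 2 = 5 to 7 + 2 = 9 days (Appendix III). Days 5, 6 and 7 fall in both. No section excludes ET samples taken without a same-day dose or flags them in the tables.

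**Timing.** Days early = nominal day of the next visit at which the assessment is due, minus the ET day. The worst case puts ET on the day after the last attended visit. The last column puts that visit at the early edge of its ±5-day window.

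| Assessment | Last visit | Mapped to | Days early, nominal | Days early, with window |
|---|---|---|---|---|
| Monthly: MADRS, CGI-BP-S, YMRS, C-SSRS, vital signs, weight, ECG | 13E, Day 330 | 14E, Day 360 | 360 − 331 = 29 | 360 − 326 = 34 |
| Two-monthly: PK, prolactin, chemistry, hematology, AIMS, BARS, SAS, HAM-A, QIDS-SR16, SDS, EQ-5D-5L, SHAPS, HbA1c, lipids, insulin, thyroid | 12E, Day 300 | 14E, Day 360 | 360 − 301 = 59 | 360 − 296 = 64 |
| Waist circumference (8E and 14E only) | 8E, Day 180 | 14E, Day 360 | 360 − 181 = 179 | 360 − 176 = 184 |

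hs-CRP has the same schedule as waist circumference, but SAP 18.2 does not clearly place it in a by-visit table, so nothing here rests on it.

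**Effect of one off-drug sample on a concentration summary.** Suppose n − 1 subjects are at level C and one is at x.

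- Arithmetic mean with x near zero: ratio (n − 1)/n. For n = 10 this is 0.90, a fall of 10%; for n = 20 it is 0.95, a fall of 5%.
- Geometric mean: ratio (x/C)^(1/n). The LLOQ for each enantiomer is 0.0500 ng/mL (SAP 19.1) and lower values are set to half, so x = 0.025.
  - Assumed C = 50: (0.025/50)^(1/10) = 0.47, a fall of 53%. With n = 20 the ratio is 0.68, a fall of 32%.
  - Assumed C = 500: (0.025/500)^(1/10) = 0.37, a fall of 63%. With n = 20 the ratio is 0.61, a fall of 39%.
  - Assumed residual of 1%: 0.01^(1/10) = 0.63, a fall of 37%.

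The levels, the residual fraction and the cell sizes are assumptions. The documents give no half-life. For assumed half-lives of 6, 12, 24 and 48 hours, the fraction left after 1 day is 6%, 25%, 50% and 71%. After 7 days it is about 4 × 10⁻⁹, 6 × 10⁻⁵, 0.8% and 9%. No size can be given for prolactin, because no on-drug or off-drug levels are stated.

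**The case against.** The strongest reply is that ET follows the Visit 14E procedures, that Appendix III lists 14E as postdose, and that ET assessments are done when the subject discontinues. Many ET samples may then follow a same-day dose. This stands as far as frequency goes: off-drug samples can enter, and how many will is unknown. It does not remove the problem, because SAP 7.4 itself admits data up to 7 days off drug. Such cases are also foreseeable. Protocol 12.4.2, for example, has a pregnant subject stop the drug and return within 48 hours.

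On size, SAP 19 gives the geometric mean only where appropriate. The mean and median are always planned; the mean moves by about 10% in a cell of 10, and the median barely moves. Falling below the LLOQ within 5 to 7 days from 50 to 500 ng/mL would need a half-life of roughly 9 to 17 hours. SAP 19 also tabulates the count below LLOQ at each visit, so such samples are partly visible. All of this stands.

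The population PK work is reported separately, with actual sample and dose times on record. Exposure duration and discontinuation by visit have their own tables, and listings keep original dates. Waist circumference is in neither document's endpoint list. These points stand and limit the reach of the concern.

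Finally, mapping ET data to the nearest visit would often collide with a visit already attended, and dropping ET values tilts the tables toward subjects who stayed. Both points shape the remedy below.

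**Conclusion.** The point holds as a labelling fault in descriptive tables. Plasma concentration and plasma prolactin summaries at an on-treatment visit can include samples that do not meet Appendix III's definition of that visit's sample. Timing errors can reach about two months for two-monthly assessments and about six for waist circumference, but only about one month for MADRS and the other monthly measures.

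A reader might infer more: that off-drug samples certainly contaminate the tables, that concentrations will be understated by half or more, or that effectiveness results in general are months out. The documents do not support this. They give no count of affected subjects, no concentrations and no half-life. The larger percentages belong to an optional statistic under assumed values, and the main effectiveness scale is monthly. The primary endpoints are incidences of adverse events, discontinuations due to them and serious events, which visit mapping does not touch, and no inference is planned. The PK and prolactin part is worth correcting because the remedy is cheap; general handling of ET timing is closer to a trade-off.

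**What to change.** In SAP 7.4 and 19, include an ET PK or plasma prolactin sample in a scheduled-visit summary only if a dose was taken that day before sampling. Otherwise show it in a separate off-drug ET row or in listings. The data exist: the last three dose times and the actual sample time are recorded (Protocol 11.5, 11.6.14 and Appendix III). SAP 4.7 drops Follow-up summaries except for the PWC, while SAP 19 keeps a Follow-up summary of concentrations; the two should be reconciled in the same edit.

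For other assessments, do not map an ET value to a planned visit when its study day is more than half the assessment interval before that visit's nominal day. At nominal spacing the limits are 30/2 = 15 days for monthly measures, 60/2 = 30 for two-monthly ones and 180/2 = 90 for waist circumference. Values beyond the limit go only into the LOCF, PCS and worst-case summaries. An ET value must never replace one from a visit already attended.

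The cost is SAP wording and a programming change. Some visits will have somewhat fewer observations, and the by-visit tables will lean slightly more toward subjects who stayed in the study.

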## 7.5. WINDOWING CONVENTIONS

No visit windowing will be performed during the analysis for this study. Data will be analyzed according

to the schedule outlined in the CSP. However, with the exception of SAE and PWC, any data collected beyond 7 days post the last OLE dose will be excluded from the efficacy and safety analyses unless otherwise specified; these data will be presented in data listings only.

## 7.6. STATISTICAL TESTS

No statistical inference will be made for this open-label extension study.

## 7.7. COMMON CALCULATIONS

Below derivation will be applied separately for both DB Baseline and OL Baseline as appropriate.

For quantitative measurements, change from Baseline will be calculated as:

- Assessment Value at Visit X - Baseline Value

For quantitative measurements, percentage change from Baseline will be calculated as:

- $(\text{Test Value at Visit X} - \text{Baseline Value}) \times 100 / \text{Baseline Value}$

## 7.8. SOFTWARE VERSION

All analyses will be conducted using SAS version 9.4 or higher.

## 8. STATISTICAL CONSIDERATIONS

### 8.1. ADJUSTMENTS FOR COVARIATES AND FACTORS TO BE INCLUDED IN ANALYSES

No statistical comparison will be conducted, so no adjustments for covariates and factors are to be considered.

### 8.2. MULTICENTER STUDIES

This study will be conducted by multiple investigators at multiple centers in the US and non-US countries, including Bulgaria, Romania, and Japan.

Center pooling will not be implemented in the analyses for this open-label extension study.

### 8.3. MISSING DATA

Individual missing items in any rating scale will not be imputed in any analysis. When calculating a total score, subscale score, or any summary scores based on more than one item, if one or more items are missing at a visit, then the associated summary score will be set to missing. For additional details, see the individual scale description sections.

- Handling of missing efficacy data, if any, is described in [Section 17.2](#).
- Handling of missing safety data, if any, is described in [Sections 18.1.1](#) and [18.6](#).
- See [APPENDIX 2](#) for details of handling incomplete/missing dates.

## 8.4. MULTIPLE COMPARISONS/ MULTIPLICITY

No statistical comparison will be conducted, so no multiplicity adjustment will be performed.

## 8.5. EXAMINATION OF SUBGROUPS

Because the small sample size, no subgroup analysis will be conducted for this study.

## 9. OUTPUT PRESENTATIONS

[APPENDIX 1](#) shows conventions for presentation of data in outputs.

The templates provided with this SAP describe the presentations for this study and therefore the format and content of the summary tables, figures, and listings to be provided separately.

## 10. DISPOSITION AND WITHDRAWALS

Unless otherwise specified, the disposition summary tables will include the following columns: PBO-SEP, SEP-SEP, and ALL EXT (all rollovers from SEP380-301).

All subjects who were enrolled in study SEP380-303 will be accounted for in this study.

Subject disposition will be presented by the actual treatment group. The number and percentage of subjects who enrolled in study SEP380-303, received at least one dose of OLE study medication, enrolled but did not receive OLE study medication, and completed or discontinued from the OLE treatment period (including reasons for discontinuation) will be presented.

Discontinuation by visit will be summarized for the enrolled subjects by the actual treatment group.

The number and percentage of enrolled subjects will also be summarized by region, country, and site, by the actual treatment group.

## 11. IMPORTANT PROTOCOL DEVIATIONS

Important protocol deviations (IPDs) will be identified and documented for all subjects based on reviews of data listings and the protocol deviations log; the data will be presented separately.

Unless otherwise specified, the IPD summary tables will include the following columns: PBO-SEP, SEP-SEP (S200-SEP and S400-SEP combined), and ALL EXT (all rollovers from SEP380-301).

The IPD categories may include, but may not be limited to:

- Did not satisfy inclusion and/or exclusion criteria for study SEP380-303.
- Received prohibited medication in study SEP380-303.

IPDs will be identified for all subjects enrolled in study SEP380-303 and presented in a data listing. The number and percentage of subjects within each IPD category will be summarized by the actual treatment for the Safety Population.

## 12. DEMOGRAPHIC AND OTHER BASELINE CHARACTERISTICS

Unless otherwise specified, the demographic and Baseline characteristics summary table will include the following columns: PBO-SEP, SEP-SEP, and ALL EXT (all rollovers from SEP380-301).

Demographic data and other Baseline characteristics will be presented for the Safety Population by the actual treatment group.

The following demographic and other Baseline characteristics will be reported for this study. According to protocol, year of birth, age, and sex collected in the core studies are re-entered into the eCRF of SEP380-303. For statistical analysis, date of birth, age, sex, race, and ethnicity will be retrieved from the ADaM datasets of studies SEP380-301. Unless otherwise specified, the categories below apply to all subjects:

- Age (years) - calculated relative to date of informed consent in SEP380-301, as a continuous variable
- Age (years) categories:
  - < 55 years
  - ≥ 55
- Sex:
  - Female
  - Male
- Race:
  - American Indian or Alaska Native
  - Asian
  - Black or African American
  - Native Hawaiian or Other Pacific Islander
  - White
  - Other
- Ethnicity:
  - Hispanic or Latino
  - Not Hispanic or Latino
- Country:
  - United States
  - Bulgaria
  - Japan
  - Romania
- Geographic region:
  - USA
  - Europe
  - Japan

- DB Baseline Height (cm), as a continuous variable
- DB Baseline and OL Baseline Weight (kg), as a continuous variable
- DB Baseline and OL Baseline BMI ( $\text{kg}/\text{m}^2$ ), as a continuous variable
- DB Baseline and OL Baseline BMI ( $\text{kg}/\text{m}^2$ ) category:
  - Underweight:  $<18.5 \text{ kg}/\text{m}^2$
  - Normal:  $\geq18.5$  to  $<25.0 \text{ kg}/\text{m}^2$
  - Overweight:  $\geq25.0$  to  $<30.0 \text{ kg}/\text{m}^2$
  - Obese:  $\geq30.0 \text{ kg}/\text{m}^2$
- DB Baseline and OL Baseline MADRS Total Score, as a continuous variable
- DB Baseline and OL Baseline CGI-BP-S Score, as a continuous variable

The following psychiatric history data will be summarized for Safety Population by the actual treatment in a separate table. All values were collected or derived in the SEP380-301 study:

- Time since initial onset of bipolar I disorder (years) - calculated relative to date of informed consent in SEP380-301
- Age at initial onset of bipolar I disorder (years)
- Time since onset of current episode of major depression associated with bipolar I disorder symptoms (months) - calculated relative to date of informed consent in SEP380-301
- Bipolar I diagnosis subtype:
  - Bipolar I disorder without rapid cycling
  - Bipolar I disorder with rapid cycling
- Number of prior hospitalizations for treatment of bipolar I disorder:
  - 0
  - 1
  - 2
  - 3
  - 4 or more
- Any other current psychiatric disorders:
  - Yes
  - No

Diagnosis and DSM-5 code for any other current psychiatric disorders will be summarized in a separate table for Safety Population. These other current psychiatric disorders will be coded using Medical Dictionary for Regulatory Activities (MedDRA) central coding dictionary, Version 22.0, and presented by System Organ Class (SOC) and Preferred Term (PT).

